Enhance Home Blood Pressure Monitoring Accuracy in uncontrolled Hypertension: a Randomized Controlled Trial

Background:

Being a highly prevalence global health problem, high blood pressure (BP) attributed to 13.5% of the global total premature death (1). Clinical findings in Hong Kong were shown to be comparable to the global situation. Locally, hypertension is the commonest chronic disease in Hong Kong with a prevalence of 27% among people aged 15 years or above. (2) It is the second commonest reason for consultation in Hong Kong primary care setting. (3) Control of BP to an optimal level is recommended to prevent irreversible cardiovascular event.

International guidelines including the European Society of Hypertension (EHS) (4), National Institute for Health and Clinical Excellence (NICE) (5) and the World Hypertension League (6) recommended appropriate use of home blood pressure monitoring (HBPM) in evaluate hypertension in certain clinical conditions. Systemic reviews have shown HBPM improve patients' BP control rate and compliance with treatment. (7,8) HBPM enables a more precise initial diagnosis of hypertension and more accurate titration of antihypertensive drug treatment (4), as shown by randomized control trials (9-12). Current Evidence suggested that blood pressure (BP) assessment are frequently inaccurate, with a high potential to misdiagnose a large segment of the population. (13). Therefore, the use of automated devices using oscillometry is recommended for HBPM (4).

As response to the recent promulgation by primary care clinicians (14), many patients with hypertension adopt HBPM (15). Local study also showed short term improvement of BP by one-off structured education program of home BP monitoring (16). However, sustainability of high quality HBPM technique remains unknown.

High quality HBPM depends on selection of validated device according to international recommendation; appropriate cuff size; conditions of measurement, correct procedure of measurement; and correct interpretation of HBPM readings. (4) Even with training, the use of standardized manual techniques (17) declines rapidly without regular retraining and accuracy testing (6). The accuracy of monitors and operators was prone to error, mostly due to mistakes by operator. (18)

Therefore, we propose to provide structural group educations focus on accurate BP measurement, provided with validated home BP device, with regular reassessment of BP measurement technique. We are interested to find out whether the proposed intervention can lower BP and sustain high quality HBPM.

Study Aims and Objectives:

We aims at comparing providing validated home BP device, followed by group education of self-BP monitoring and regular assessment accuracy of BP monitoring, which may possibly improve BP control rate of patients with uncontrolled hypertension in primary care setting. We would also like to evaluate whether the quality of BP measurement is sustainable, any change in biochemical markers, clinic BP readings in 6 months, 12 months and 18 months interval. We would also find out patients' view on home BP monitoring and the education program.

Research Questions

1. Do the people with uncontrolled BP have higher control rate after provision of validated BP device followed by education and assessment of BP measurement technique?
2. Are there improvements in the clinic BP body weight, BMI, biochemical markers followed by the HBPM education program?
3. Can quality of HBPM be sustainable by education followed by regular reassessment?
4. What is patients' view on HBPM?

Methods

We adopt prospective longitudinal randomized control trial. Subjects from four general outpatient clinics (GOPCs) located in urban residential area will be involved in the study.

Study Practices and randomization procedure

We aimed to determine the effectiveness of HBPM education and provision of validated home BP device. Since the intervention involve doctors, nurses and patient cooperation, cluster (using one clinic as one cluster) approach is utilized to minimize risk of treatment contamination. Three clinics are randomly assigned as intervention clinic and the other three will be assigned as usual care clinic. (Appendix 1) To avoid contamination, separate protocols will be sent to individual clinics assigned to intervention and control. The Research helper will assist subject recruitment and data collection. The measurements and lab test will be performed by local clinic nurses and doctors in control clinics.

Research Subjects Recruitment

The recruitment of subjects and study workflow is shown in **Figure 1**. We include adult subjects aged above 18 years old on hypertensive treatment more than 12 months with uncontrolled hypertension and no previous HBPM on the day of recruitment. Uncontrolled hypertension is defined as BP > 140/90mmHg(19,20) in subjects age < 80; and BP > 150/90mmHg(21) in subjects age ≥ 80 . They will be invited to participate if they are willing and capable to perform home BP monitoring by themselves on daily basis. Appropriate subjects will be identified during doctor consultation and nurse consultations and subjects will be invited after normal consultation.

We exclude subjects who are unable to perform the home monitoring either by themselves; or have arrhythmias, unstable angina, serum creatinine > 250 mmol/l, orthostatic hypotension, severe left ventricular impairment, severe aortic stenosis and pregnancy.

Data Collection

Subjects enrollment and baseline assessment take place before randomization. Follow up data collection will be conducted 6 months, 12 months and 18 months after intervention.

Baseline Assessment

At baseline, patient age, sex, smoking habits, body mass index, waist circumference, education level, occupation, payment method, household income and number of household family members, health literacy by Chinese Health Literacy Scale for Chronic Care (22) will be collected via questionnaires by clinic nurses and research helper. Medical history includes diabetes mellitus, nephropathy, manifest cardiovascular disease (namely ischaemic heart disease, cerebral vascular disease, and peripheral vascular disease), current medication including antihypertensives drugs, lipid lowering agents, and antiplatelet drugs, laboratory test results including fasting blood sugar, glycemic haemoglobin level, lipid profile, serum creatinine level, presence of significant proteinuria will be collected by investigators via computerized patient record.

Baseline blood pressure will be measured in clinic 3 times after taking at least 5 minutes rest in a sitting position by Ormon HEM-907 clinic use BP device (passed International Protocol of the European Society of Hypertension for elderly)(23); with an appropriately sized cuff in the right arm, which is accredited model by British Hypertension society. The BP will be taken at least one hour after the subject's last meal and at least 30 minutes after smoking or consumption of a caffeinated beverage. The systolic and diastolic blood pressure will be measured 3 times and we will take the mean of the second 2 out of 3 office reading each time).

For safety considerations, if any BP measurements were above 170 mmHg systolic or 105 mmHg diastolic, the BP were rechecked again 5 minutes later. If the BP remained above these levels, the result will alert attending physicians for further management.

Usual Care (Control Group)

All subjects see their physicians and / or nurse for routine BP measurement and /or adjust medication at the discretion of the health professional. They received nurse individual counselling explained management of uncontrolled hypertension in patients' understandable language will be arranged as routine practice.

Intervention Group

1. Two 2 hours Training sessions (by nurses/ doctors)

All subjects will attend a 2 hours training in the education room of study clinics. There will be 15 to 30 subjects in each education group, depends on size of venue.

Nurses or doctors will brief subjects about basic hypertension medical knowledge, lifestyle modifications and hypertensive complications for 30 minutes. Automated Brachial type home BP device AND UA651 (Appendix 5) will be loaned to subjects up to 3 months.

It follows by 1 hour interactive seminar

1. Select appropriate cuff size by nurses
2. Stepwise education on home BP monitoring procedure
3. Standard Home BP Record Hand Book (Appendix 6).
4. Method of recording

Finally, it will be demonstration of assessment of the HBPM procedure. (Appendix 7) All subjects will undergo the same assessment when they return the BP device.

2. Next scheduled clinic visit (1-3 months after Training Session)

- In the next doctor consultation (within 12 weeks of education talk), BP device will be returned
- Clinic nurses will assess the self-monitoring technique, home BP records , body weight and BMI and the clinic BP levels

3. 6 months, 12 months and 18 months post intervention

Clinic nurses will assess the self-monitoring technique, home BP records, body weight and BMI and the clinic BP levels

4. 18 months post intervention

The above measurement will be collected via questionnaires by clinic nurses and research helper. Medical history includes diabetes mellitus, manifest cardiovascular disease (namely ischaemic heart disease, cerebral vascular disease, and peripheral vascular disease), current medication including antihypertensives drugs, lipid lowering agents, and antiplatelet drugs, laboratory test (6 to 18 months post intervention) results including fasting blood sugar, glycemic haemoglobin level, lipid profile will be collected by investigators via computerized patient record.

Data analysis

The Outcome Measurement includes

1. Blood pressure control rate (Primary outcome)
2. Change in clinic mean systolic and diastolic BP between baseline and each of the follow up point
3. Accuracy of HBPM by standard checklist in 1-3 months and 9-12 months post-intervention
4. Practice of HBPM 6-months post-intervention
5. Change in biochemical markers

6. Change in Body Weight and BMI
7. Adverse effect (reported by research subjects)

Sample size calculation will be based on the mean difference in blood pressure between intervention and controls at 9-12 months after baseline. Accounting for the clustering effect by practice, the intraclass correlation (ICC) for the intra-cluster correlation in primary care setting was taken as 0.01 which was a median estimate reported in previous study (24). In order to have 80% power and 5% false positive error to detect a difference in blood pressure of 3mmHg with assumed standard deviation of 5mmHg, there will be 216 subjects (25) which will be obtained by sampling 6 general outpatient clinics randomly, with 36 subjects each clinic in intervention group and 36 subjects each clinic in control group. Assuming 20% of attrition rate for 6-12 months follow-up, we need to recruit 45 subjects in each group per clinic at baseline, in total of 270 subjects.

Descriptive statistics including mean, standard deviation of continuous outcomes and proportion of dichotomous outcomes will be calculated. Primary analysis will be an intention-to-treat analysis of the difference in outcomes between groups at 6-18 months after baseline. As with repeated measurement for patients, generalized estimating equation models using identify link will be conducted to assess differences in continuous outcomes within-group and between groups, adjusting for baseline patients' characteristics and clustering of patients per practice. Generalized estimating equation models using logistic link will be conducted to analyze differences within-group and between groups for dichotomous outcomes, adjusting for same sets of patients' characteristics. Missing values will be imputed using last value carrying forward method. Repeated analysis will be done for per-protocol analysis.

All statistical analyses will be performed using SPSS Windows 21.0 program. P-value less than 0.05 will be considered statistically significant.

Data collection throughout the trial

Demographic Questions	Measurements
Duration of HT	BMI (BH/ BW)
Past Medical history	Waist circumference
Contra-indications to antihypertensive drugs	Clinic BP (sitting position/ standing position)
Current HT medication	Lab Test: FBS, Lipid profile, eGFR, Urine PCR
	HBPM Technique

Qualitative Study on Evaluation of the Programme

Individual interviews (30-45 minutes) to 30 subjects from intervention group will be performed 2-4 months after education seminar and 1st doctor consultation (whenever later). Views on the self-monitoring, home BP reading interpretation blood pressure treatment targets, will be collected.

Sampling Method: 30 subjects with uncontrolled hypertension, some have attended intervention group, with different sex, age group, health literacy and occupations will be interviewed.

Semi-structured interview guide for patients and their family caregivers using social cognitive theory(26) as framework

Framework	Interview questions
Overall experience & attitude	Does high blood pressure (BP) border you? Why? Tell us about your general impression on Self-blood pressure monitoring (SBPM)
Self-monitoring mechanism - Value of Behaviour - Motivation	Why do think it is important / not important for SBPM? Probing 1: (if important) What do you expect from SBPM? How and Why? Probing 2: (if not important) What are more important than SBPM in your disease management? Is there any particular person, or reason, asked you to perform SBPM regularly?
- consistency	Do you get your BP checked regularly? How to do it? Probing: Where? Who? What is / are the machine(s)?
- temporal proximity - self-diagnosis	Do you notice anything will affect the SBPM readings? What was your observation? What do you think was the relationship? Do you think the BP readings means anything? probing 1: such as have, or have no health problem probing 2: where did you learn that BP reading means problem/no problem? Tell me more about that
Self-judgment mechanism - Self-comparison	You have measured many BP readings at home. How's the BP reading change in different time of the day/ over a period time? What do you think was the reasons of your BP variation?
- Social comparison	How were your BP readings when compare with your friends or family, or other patients? How do you feel about that? Why do you have that feeling?
- Statistical comparison	Do you know what is the standard BP target readings? How did you acquire the BP level? Do you think your BP is up to standard? Why?
- Education - Modelling	How did you learn SBPM? Tell me about your experience

	
Do think your SBPM technique is correct? How did you do it at home?
 
Probing: (if not correct) Did anyone comment on your SBPM technique, can you share the comment with me?
 
Did you observe anyone else how to measure BP?
 
Probing: How did you feel about learning SBPM?

Self-evaluation mechanism	
Are you happy with/ worry about your SBPM readings so far?
 
What are you goal? (aim or target from SBPM)

- Self-satisfaction	
- Self-incentives	
If any, what are the benefit of SBPM?
 
(Negatively, what are the unwanted or negative effects of SBPM?)
 
Why?

- External Reward	Any tangible benefits of SBPM regularly? Can you describe?
Overall Comment on Education program	
(If attended before)
 
What is your comment on the RAMP education program?
 
Have you learnt anything new? Do you change (your behaviour) after attending the program?

References

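### The loaned BP device goes back within 12 weeks, yet home BP records are reviewed at 6, 12 and 18 months with no stated device source and no rule for patients without one

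*Protocol*

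**What the plan says.** All statements are in the Protocol.

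- **Entry (Research Subjects Recruitment).** Patients have "no previous HBPM on the day of recruitment". They must be "willing and capable to perform home BP monitoring by themselves on daily basis". Owning or obtaining a device is not a condition.
- **Loan (Intervention Group, item 1).** The device "will be loaned to subjects up to 3 months".
- **Return (Intervention Group, item 2).** "In the next doctor consultation (within 12 weeks of education talk), BP device will be returned". Technique is assessed in all subjects at that point.
- **Later visits (Intervention Group, item 3).** At "6 months, 12 months and 18 months post intervention" the instruction is: "Clinic nurses will assess the self-monitoring technique, home BP records, body weight and BMI and the clinic BP levels".
- **Objective (Research Questions, question 3).** "Can quality of HBPM be sustainable by education followed by regular reassessment". Study Aims and Objectives and the text just before it also set out to learn whether good HBPM lasts. The Background makes a validated monitor and a suitable cuff part of what high quality means, alongside measurement conditions, procedure and interpretation.
- **Outcomes (Data analysis).** Outcome 3 is "Accuracy of HBPM by standard checklist in 1-3 months and 9-12 months post-intervention". Outcome 4 is whether HBPM is practised at 6 months.
- **Missing data (Data analysis).** Missing values are filled by last observation carried forward (LOCF), with no exception for HBPM items.

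**The concern.** The trial supplies the means of home measurement for the first 12 weeks or so, then looks for the product of home measurement for another 15 months. The visible text does not bridge the gap. It names no device source after return, does not ask patients to obtain one, does not have their access to one recorded, and does not say how patients without one are counted. The table of data collected throughout the trial lists HBPM technique but nothing about the device.

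Two things are at stake, both concerning the sustainability question. First, late home records will come from a self-selected group that has found another device of unknown model and cuff, although the Background treats both as components of quality. Second, if a patient without a device is treated as having a missing value, LOCF can supply the value recorded while the patient still held the trial device. The loss of home monitoring, which is what the question asks about, would then be hidden by early performance.

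**Working it through.** The protocol gives no figure of its own on this point. The check compares its calendar with its list of assessments.

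**1. Timing.** Inputs: return within 12 weeks (item 2), loan of at most 3 months (item 1), visits at 6, 12 and 18 months (item 3).

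- 12 weeks = 84 days; 84 / 30.4375 = 2.76 months.
- Gap from return at 12 weeks to each visit: 6 − 2.76 = 3.24 months; 12 − 2.76 = 9.24 months; 18 − 2.76 = 15.24 months.
- Taking the full 3 months instead, the gaps are 3, 9 and 15 months.
- Share of follow-up with the trial device: at most 3/18 = 17%. Share without it: at least 15/18 = 83%.
- The later checklist window opens at 9 months, which is 9 − 2.76 = 6.24 months after return.

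Every 6-, 12- and 18-month review of home records therefore falls after the trial device has been given back.

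**2. What each measure needs.**

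| Measure | Needs a home device after month 3? | Observable in |
|---|---|---|
| Home BP records at 6, 12, 18 months | Yes | Only patients with access to another device |
| Validated model and suitable cuff in home use | Yes | Only patients with access to another device |
| Checklist technique | No, done by clinic nurses | All attenders |
| Practice of HBPM at 6 months | No, not practising is a valid answer | All attenders |
| BP control rate and clinic BP | No | All attenders |

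The conflict is confined to the first two rows.

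**3. How many patients this could touch.** The protocol gives no rate of later device access, so this is an illustration over an assumed range. The sample size paragraph plans 36 evaluable subjects per clinic. With three intervention clinics, as the randomization section states, that is 3 × 36 = 108.

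| Assumed access to another device | Could supply late home records | Could not |
|---|---|---|
| 20% | 0.20 × 108 ≈ 22 | ≈ 86 |
| 30% | 0.30 × 108 ≈ 32 | ≈ 76 |
| 50% | 0.50 × 108 = 54 | 54 |
| 70% | 0.70 × 108 ≈ 76 | ≈ 32 |

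The last column is the most patients for whom LOCF could replace an absent late record with a loan-period one. It applies only if absence is coded as missing; if it is coded as not monitoring, LOCF does nothing. The protocol does not say which coding is meant.

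**The case against.** The strongest reply is that the sustainability question is answered by the checklist. Outcome 3 is a nurse-assessed skill test, first given to all subjects at device return, and nothing limits the later test to device owners. Outcome 4 can also be recorded in everyone. This stands. A reader might infer that sustained HBPM can be observed only in patients who buy a device, and the document does not support that. Technique and practice remain open to all attenders, and buying is only one route: a household or borrowed device is equally possible, and the text is silent.

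A reader might also infer that patients without a device are dropped from the analysis. No text says so; the stated approach is intention-to-treat with imputation. The risk lies in the imputation.

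Nor is the primary outcome compromised. BP control rate is measured in the clinic, and education with a short loan is a legitimate package to test, openly described under Intervention Group.

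Finally, Figure 1, the appendices and any SAP are not shown, and denominators for secondary outcomes are often left to a SAP. That limits what can be said about missing detail. It does not remove the conflict, because the visible text explicitly requires the device back and explicitly schedules the later record reviews. A SAP also cannot restore device access that was never recorded at the visits.

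**Conclusion.** The concern holds in limited form. The loan period and the 6-, 12- and 18-month home-record reviews do not fit together as written. The trial device is absent for at least 15 of 18 months, and all three reviews fall at least 3, 9 and 15 months after its return. From then on, home records and the device and cuff components of quality are observable only in patients with access to another device. LOCF as stated could credit the rest with loan-period values and so overstate sustained HBPM.

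The size of any overstatement cannot be derived from the document; it depends on later device access and on how an absent record is coded. The calendar finding needs no assumption beyond the visible text being complete on device supply. The matter affects a named research question and secondary measures, and should be put right, but it does not touch the primary BP comparison.

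**What to change.** 1. Reconcile the loan period with the home-record reviews at 6, 12 and 18 months, so that the protocol says what those records are expected to come from.
2. At each of these visits, record whether the patient has access to a home device, its model (validated or not) and its cuff size.
3. Report sustained home monitoring over all intervention patients. Count those seen with no device or no home records as not sustaining, and do not carry loan-period values forward for this item. Show patients not seen at a visit separately, since their status is unknown.
4. Report checklist technique for all attenders, and also split by device access.
5. Describe the tested package, in the aims and in any conclusion, as education, a device loan of up to 3 months and reassessment, so that neither a positive nor a null result is read as evidence on continuing provision of a device.

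The cost is a few extra items on an existing visit form and a wording change. No extra patients or visits are needed. The sustainability figure will probably be less favourable.

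### Last value carried forward can draw on a 1-3 month clinic BP that the text schedules only in the intervention arm, which tilts the control rate towards the intervention

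*Protocol*

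**What the plan says.** - **Early clinic BP, intervention arm.** Intervention Group, item 2, is headed "Next scheduled clinic visit (1-3 months after Training Session"). Its content is: "Clinic nurses will assess the self-monitoring technique, home BP records , body weight and BMI and the clinic BP levels".
- **Control arm.** Usual Care (Control Group) gives no dated measurement before 6 months: "All subjects see their physicians and / or nurse for routine BP measurement and /or adjust medication at the discretion of the health professional".
- **Common follow-up.** Data Collection: "Follow up data collection will be conducted 6 months, 12 months and 18 months after intervention".
- **Outcomes.** Data analysis lists "Blood pressure control rate (Primary outcome") and, second, "Change in clinic mean systolic and diastolic BP between baseline and each of the follow up point".
- **Primary analysis.** "Primary analysis will be an intention-to-treat analysis of the difference in outcomes between groups at 6-18 months after baseline".
- **Missing data.** "Missing values will be imputed using last value carrying forward method". Nothing says which recorded values qualify as the last value.
- **Entry.** Under Research Subjects Recruitment, every subject has uncontrolled BP on the day of recruitment: above 140/90 mmHg under age 80, above 150/90 mmHg from age 80.

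**The concern.** When both arms are measured on the same schedule, carry-forward with equal dropout and no effect produces no difference between arms, whatever its other faults. Here the schedules in the text differ by one early reading, and the imputation rule does not exclude it.

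For a control subject with no 6-month value, the last study value is baseline. Because of the entry criterion, that is nearly always a failure on the primary outcome. For an intervention subject who attended at 1-3 months, the last value is a later reading, and some of those are controlled through regression to the mean and ordinary care alone. For the control rate, the direction is set by the entry rule: replacing a near-certain failure with a later reading can hardly do anything but raise the rate. What is at stake is a spurious gain in the primary outcome and a smaller one in mean BP.

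**Working it through.** **The plan's own figures.** The protocol gives no figure for this effect. Its sample size figures supply the attrition, ICC and arm size used below, and they reproduce. With 3 clinics per arm, 36 subjects per clinic, ICC 0.01, SD 5 mmHg, difference 3 mmHg and two-sided 5% (sidedness assumed), the design effect is 1 + 35 x 0.01 = 1.35. Power from a noncentral t with 4 degrees of freedom is 0.807 at 36 per clinic and 0.799 at 35, hence 6 x 36 = 216. Attrition: 216 / (1 - 0.20) = 270, or 135 per arm.

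**Set-up.** Assume no treatment effect and the same dropout in both arms. Let
- d = share lost after the 1-3 month visit and before the 6-month visit;
- e = share lost before the 1-3 month visit;
- p = share controlled on any repeat measurement, the same in both arms;
- q = share whose recorded baseline counts as controlled.

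Subjects lost after 6 months carry a shared visit in both arms. Subjects in e carry baseline in both arms. Only d differs:
- intervention: (1 - d - e)p + dp + eq
- control: (1 - d - e)p + dq + eq
- difference: d(p - q), which is d x p when q is close to 0.

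The same difference appears at 6, 12 and 18 months, since these subjects have carried values throughout.

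**Control rate.** d and p are assumptions; the documents give neither.
- d = 5%, p = 20%: 0.05 x 0.20 = 0.01, or 1 point.
- d = 10%, p = 30%: 0.10 x 0.30 = 0.03, or 3 points.

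Letting d be a fraction f of the protocol's 20% attrition, with p from 0.2 to 0.5:

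| f | d | Spurious difference |
|---|---|---|
| 0.25 | 5% | 1.0 to 2.5 points |
| 0.5 | 10% | 2 to 5 points |
| 1 | 20% | 4 to 10 points |

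An illustrative simulation of regression to the mean alone (true systolic mean 138 and SD 12, within-person SD 5 to 10, selected above 140, all assumed) put 20% to 33% at or below 140 on repeat. That supports the lower part of the p range but leaves out any improvement from usual care.

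**Effect on the test.** At p = 0.3 the expected rates are 27.0% control and 30.0% intervention for f = 0.5, and 24.0% and 30.0% for f = 1. With 135 per arm, design effect 1 + 44 x 0.01 = 1.44 and a normal approximation, the two-sided rejection rate rises from 5% to about 7% and 15% respectively. At f = 0.25 and p = 0.2 it is about 5.3%.

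**Mean BP.** The bias is d times the fall by 1-3 months. The simulation gave falls of 1.7 to 5.6 mmHg. Rounding to 2 to 6 mmHg, d = 10% gives 0.10 x 2 = 0.2 to 0.10 x 6 = 0.6 mmHg, which is 7% to 20% of the 3 mmHg design difference.

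**After the fix.** If both arms carry forward only from shared visits, the d subjects carry baseline in both arms and the difference is 0.

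**The case against.** Much of the case on the other side stands.

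- **The comparison is already confined to 6-18 months.** A reader might infer that the unequal schedule itself biases the between-group analysis. The documents do not support that. The primary analysis is set at 6-18 months, Data Collection names 6, 12 and 18 months, and the follow-up points in the second outcome are most naturally those visits. A visit for returning the device and checking technique does no harm by itself. The problem arises only when its BP fills a later gap.
- **The protocol does not say that the 1-3 month value is carried.** True, and an unseen SAP may exclude it. But the protocol does more than stay silent: it states a rule, and on its plain reading the last value includes this one.
- **The control schedule is not fully visible.** Figure 1 is not shown, and the separate protocols for intervention and control clinics are not at hand. One cannot say that controls have no early reading, only that the text schedules none. Routine readings may exist in clinic records, but they are undated and not named as study data. Using them would still leave the last value differently defined by arm.
- **Not every early leaver is affected.** Those lost before the 1-3 month visit carry baseline in both arms.
- **A controlled baseline is possible.** Baseline is the mean of the last two of three readings and may differ from the reading that qualified the subject. This makes q slightly above 0 and reduces the bias without removing it.

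**Conclusion.** The point holds as a defect of the carry-forward rule in combination with the intervention-only early BP. Followed literally, the rule favours the intervention on the primary outcome even with no effect and identical dropout.

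A plausible size is about 1 to 3 percentage points in control rate and, at d = 10%, 0.2 to 0.6 mmHg in mean BP. It rests on three assumptions: that the 1-3 month value is eligible to be carried, that controls have no matching study value, and the chosen d and p. If few subjects are lost between the two visits, the effect is negligible.

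A reader might infer a much larger distortion, such as 8 points (d = 20%, p = 40%) or up to 1.6 mmHg (d = 20%, fall of 8 mmHg). The documents do not support this as an expectation. It needs all the attrition to fall between the 1-3 and 6 month visits, whereas the protocol states its 20% for 6-12 months of follow-up. Both p = 40% and the 8 mmHg fall also exceed what the simulation of regression to the mean gave. These are upper-end cases. The change should be made because it is nearly free, not because the bias is known to be large.

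**What to change.** In the missing-data sentence of the Data analysis section, state that any carry-forward for between-group BP outcomes uses only baseline and the visits scheduled in both arms (6, 12 and 18 months). Add that the intervention-only 1-3 month clinic BP is descriptive and never replaces a missing 6, 12 or 18 month value. If Figure 1 or the control clinics' own protocol does schedule an early BP for controls, say so in the main text instead and treat that visit alike in both arms; the artefact is then also zero.

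The cost is one or two sentences, with no new visit and no new data. The downside is that one observed value is not used for some intervention subjects. It remains available for describing the programme.
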